**MC2-01-C6_STATISTICAL ANALYSIS PLAN_Final 3.0_07 September 2020**

dose of study therapy or is ongoing at the end of clinical study, then the condition/diagnosis will be classified as Concurrent. If the information about stop date of condition/diagnosis is missing or incomplete, the rules from section 6.3 will be applied for classification. Medical history record will be assumed to be Concurrent, unless there is clear evidence (through comparison of partial dates) to suggest that the condition/diagnosis stopped prior to the first dose of study therapy. If there is clear evidence to suggest that the condition/diagnosis stopped prior to the first dose of study therapy, the condition/diagnosis will be assumed to be Prior.

All data will be listed.

7.5. Prior and Concurrent Medications⁶

eCRF form: “PRIOR/ CONCOMITANT THERAPY AND NON-DRUG THERAPY”.

All medications, including OTC drugs, herbals, vitamins, dietary supplements etc., taken within 30 days prior to the start of the trial will be recorded at Screening (SV1 and/or SV2). Thereafter, a record of all medications and supportive therapy taken during the trial will be made.

All prior and concomitant medications (including non-drug therapy) will be coded using the World Health Organization Drug Dictionary (WHODD) version B2 September 2018 (or more recent version if available) according to Data MATRIX SOP [4]. The number (%) of subjects reporting the use of any prior or concomitant medication will be presented in tables by pharmacological subgroup (3rd level) and chemical substance (5th level). Post-treatment medications will be reported in listing only.

Classification of treatment as either Prior, Concomitant or Post-Treatment will be based on start and stop date of medication in “PRIOR/CONCOMITANT THERAPY AND NON-DRUG THERAPY” eCRF form.

Medications that stop prior to the date of first dose of study therapy will be classified as Prior medications. If a medication stops on or after the date of first dose of study therapy (or “ONGOING”) then the medication will be classified as Concomitant unless the medication started after the date of last IMP administration in which case it will be classified as Post-Treatment. If the information about stop date of medication is missing or incomplete, the rules from section 6.3 will be applied for classification. Medications will be assumed to be concomitant, unless there is clear evidence (through comparison of partial dates) to suggest that the medication stopped prior to the first dose of study therapy or started after the last dose of study therapy. If there is clear evidence to suggest that the medication stopped prior to the first dose of study therapy, the medication will be assumed to be Prior. If there is clear evidence to suggest that the medication started after the last dose of study therapy, the medication will be assumed to be Post-Treatment. By-patient listings will be provided with appropriate flagging of prior, concomitant and post-treatment records.

⁶ This section is based on the section 7.2 “Prior and Concomitant Medication” of clinical study Protocol.

**MC2-01-C6_STATISTICAL ANALYSIS PLAN_Final 3.0_07 September 2020****7.6. Prior and Concurrent Procedures**

eCRF form: “PRIOR/ CONCOMITANT PROCEDURES”.

Procedures will be coded using the Medical Dictionary for Regulatory Activities (MedDRA) version 22.0 (or more recent version if available) according to Data MATRIX SOP [4].

All procedures recorded will be listed.

8. Efficacy Analyses

Not Applicable.

9. Safety Analyses**9.1. Exposure⁷**

Exposure and compliance will be evaluated based on the information from the “STUDY DRUG APPLICATION”, “STUDY DRUG COMPLIANCE”, “STUDY DRUG ACCOUNTABILITY”, “END OF TREATMENT”, “MISSING DOSES” eCRF form.

Subjects are to apply the IP topically once daily, preferably in the evening, for 8 weeks. The subject should apply enough IP to treat the entire affected areas and rub in gently to ensure that the plaques are saturated with the medication. Up to 3 tubes of 60 gram will be dispensed for a treatment period of two weeks including the allowed visit window of 2 days.

Only affected areas are to be treated. The subjects should therefore not continue treatment on a skin area which has been cleared but treatment may be restarted in case of recurrence at the subjects’ discretion.

Dose modification can only occur after Week 4.

Subjects classified as clear at any of the on-treatment visits may stop the IP treatment at the investigator’s discretion. They should remain in the trial and attend all visits up to and including the follow-up visit. The IP will continue to be dispensed to the subject, and IP treatment may be restarted at the subject’s discretion. The subject should not discontinue treatment themselves between visits but is only allowed to stop using the IP treatment on the advice of the investigator at a scheduled visit.

The total duration of exposure is defined as the time interval in days between the first dose and the last dose, inclusive, of study drug as [(date of last dose – date of first dose+1)].

Total dose (g) administered during the study will be assessed based on study drug accountability data as [average weight of tube dispensed – weight of tube returned] summed over all tubes dispensed except for tubes assessed as unused or used but lost which will not be taken into account in the calculation. Average dispense weight is 75.54 g.

⁷ This section is based on the section 6.2 “Dosing Regimen” and 6.3 “Dose Modification” of clinical study Protocol.

**MC2-01-C6_STATISTICAL ANALYSIS PLAN_Final 3.0_07 September 2020**

Average weekly dose (g) will be calculated as [total dose (g) / (total duration of exposure / 7)].

Compliance will be estimated as [100% * (number of required days in the time period assessed – number of missed doses during the time period assessed) / number of required days in the time period assessed]. The number of required days is the total number of days between the first and the last application in the time period assessed excluding days with approved IMP discontinuation.

If a dose is missed due to approved discontinuation at a given day this day will not be included in the calculation of compliance. The period of time between the approved discontinuation at a scheduled visit and treatment restart (not inclusive) will not be taken into account in the calculation of compliance.

Treatment compliance will be categorized to less than 80% versus 80% or more.

Extent of exposure (days) will be calculated as [number of required doses - total number of missed doses]. The number of required doses is the total number of days between the first and the last application in the time period assessed excluding days with approved IMP discontinuation.

Number of missed doses will be summarized for subjects with at least one missed dose as a continuous variable, both using zero counts for those subjects from Safety Population who have not reported any missed dose and providing summary only for those subjects who reported at least one missed dose.

Total duration of exposure (days), total dose (g), weekly dose (g), treatment compliance (%), extent of exposure (days), number of missed doses will be summarized by time period (up to Week 2, up to Week 4 and Week 4 to Week 8) and for the entire treatment period to the Week 8 visit, using descriptive statistics in the Safety population.

The periods that the kits were used as recorded on “STUDY DRUG ACCOUNTABILITY” eCRF form will be used to assign the kit to one of the time periods for calculation of total dose (g) administered during each period (up to Week 2, up to Week 4 or Week 4 – Week 8). If the use period starts at Week 4 or Week 6 visit the time period is Week 4 to Week 8, if the use period starts before Week 2 (Week 4) and ends on or before Week 2 (Week 4), the time period is up to Week 2 (Week 4), otherwise time period cannot be determined.

The periods’ start and end date will be defined through the actual dates of subject’s visits. Week 2 (Week 4) visit date will be considered the last day of Week 0 – Week 2 (Week 4) period.

All exposure data will be listed by study period.

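### SAP 9.1 counts required days and missed doses over different windows, so compliance is ambiguous after a self-stop or a boundary gap; a used-but-lost tube understates weekly dose

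*SAP*

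**What the plan says.** SAP 9.1 computes compliance as required days minus missed doses, divided by required days. For the denominator, "The number of required days is the total number of days between the first and the last application in the time period assessed", with days of approved discontinuation removed. Extent of exposure starts from the same first-to-last span and subtracts the total number of missed doses.

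The missed doses in the compliance formula are those falling in the period assessed. SAP 9.1 sets the period limits by actual visit dates: the Week 2 or Week 4 visit day closes the period that leads up to it. Exposure, compliance and missed doses are tabulated up to Week 2, up to Week 4, for Week 4 to Week 8, and for the whole treatment period. "Treatment compliance will be categorized to less than 80% versus 80% or more".

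A stop by the subject alone is not an approved discontinuation: the subject "is only allowed to stop using the IP treatment on the advice of the investigator at a scheduled visit". For approved stops, "The period of time between the approved discontinuation at a scheduled visit and treatment restart (not inclusive) will not be taken into account".

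Total dose sums dispensed minus returned tube weight over all dispensed tubes, "except for tubes assessed as unused or used but lost which will not be taken into account in the calculation". Average weekly dose divides that total by the full duration of exposure in weeks.

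**The concern.** Numerator and denominator should cover the same days. Here the denominator stops at the last application in the period, while the missed-dose count is tied to the visit-defined period. The two agree when the subject applies the product on the first and last planned days of the period. They part when an unapproved gap touches either end.

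The SAP does not say whether a missed dose before the first or after the last application is subtracted. If it is not, unapproved days drop out just as approved days do, and the compliance row cannot show them. If it is, doses are subtracted from a span that never contained them, and the result is too low or negative.

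The tube rule has a different fault. Zero grams is correct for an unused tube and wrong for one that was used and then lost. Because the days remain in the denominator, the error in weekly dose can only be downward.

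In a maximum-use trial, compliance and grams per week tell the reader what exposure lies behind the HPA-axis and calcium results.

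**Working it through.** The SAP states no numerical result to reproduce, so its formulas are applied to nominal days.

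**Inputs.** The SAP section 7 visit windows put the first application on study day 1 and the Week 2, 4 and 8 visits on days 15, 29 and 57. Protocol 7.6.5 has no application on the Week 8 visit day, so the last planned dose is day 56. Planned doses are therefore 56 overall, 29 up to Week 4 (days 1-29) and 27 in Week 4 to Week 8 (days 30-56).

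**Formulas.** Compliance = 100 x (required - missed) / required. Two readings of missed doses are possible:
- span-only: only those between the first and last application in the period;
- whole-period: all those in the visit-defined period.

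The comparator is doses applied divided by planned doses.

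**Self-stop after day 42 (days 43-56, 14 doses, not applied).** Required days are 42 overall and 13 in Week 4 to Week 8 (days 30-42).

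| | Overall | Week 4 to Week 8 |
|---|---|---|
| Span-only | 42/42 = 100% | 13/13 = 100% |
| Whole-period | (42-14)/42 = 66.7% | (13-14)/13 = -7.7% |
| Share of planned doses | 42/56 = 75.0% | 13/27 = 48.1% |

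Extent of exposure under the whole-period reading is 42 - 14 = 28 days overall and 13 - 14 = -1 day in Week 4 to Week 8, although 42 and 13 doses were applied.

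**Unapproved gap on days 30-35 (6 doses).** In Week 4 to Week 8 the applications run from day 36 to day 56, which is 21 days.
- Span-only: 21/21 = 100%.
- Whole-period: (21-6)/21 = 71.4%.
- Share of planned doses: 21/27 = 77.8%.
- Overall, either reading: (56-6)/56 = 89.3%, because the gap is then interior.

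Under the span-only reading this subject shows 100% up to Week 4 (29/29), 100% for Week 4 to Week 8, and 89.3% overall.

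**The 80% class, overall, for a self-stop after day d.**
- Share of planned doses is d/56: 44/56 = 78.6% and 45/56 = 80.4%.
- Span-only always gives 100%, so stops up to day 44 are classed too high.
- Whole-period gives (2d-56)/d: 36/46 = 78.3% and 38/47 = 80.9%. Stops after day 45 or 46 are then classed too low.

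**Lost tube.** Understatement of weekly dose = grams used from the tube / (duration / 7). The upper bound takes the full 60 g stated content and a duration that fills the period:
- entire treatment, 56 days: 60/(56/7) = 7.5 g/week;
- up to Week 4, 29 days: 60/(29/7) = 14.5 g/week;
- Week 4 to Week 8, 27 days: 60/(27/7) = 15.6 g/week;
- up to Week 2, 15 days: 60/(15/7) = 28 g/week.

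If little of the tube was used, the understatement approaches zero. If the subject's duration is shorter than the period, the weekly figure is larger.

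**The case against.** A reader might infer that a self-stop simply scores 100% compliance. The documents do not support that as a fact. Neither SAP 9.1 nor the footnote to Table 14.1.13.1 limits missed doses to the application span. The compliance formula taken literally subtracts every missed dose in the visit-defined period, which puts both worked examples below 80% in Week 4 to Week 8. The 100% score, and the placing of stops up to day 44 in the upper class, arise only under the span-only reading. That reading is plausible because it keeps extent of exposure from going negative, but it is not stated. Whether days after a self-stop are entered on the missing-doses form cannot be seen from these documents.

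A reader might also infer that these events are hidden outside the listings. They are not. The same table carries rows for total duration, extent of exposure and missed doses. A day-42 stop shows as a duration of 42 days overall and 13 in Week 4 to Week 8. Table 14.1.1 counts treatment stopped before the Week 8 visit, with reasons. Listings 16.2.1.4, 16.2.5.3 and 16.2.5.4 give treatment completion, missed doses and tube accountability. Footnotes to Table 14.1.13.1 and Listing 16.2.5.1 disclose that lost tubes are left out of total dose.

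This limits the consequence but does not remove the fault. Neither reading returns the share of planned doses, and disclosing the omission from total dose does not correct the weekly dose.

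**Conclusion.** The concern holds as an ambiguity in one derivation and a one-directional error in another. For a day-42 self-stop, compliance can be reported as 100% or 66.7% overall, against 75.0% of planned doses. For Week 4 to Week 8 it can be 100% or -7.7%, against 48.1%. A used-but-lost tube understates weekly dose by at most 7.5 to 28 g per 60 g tube, depending on the window.

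The severity is minor. Only descriptive exposure tables are affected, and no endpoint or analysis population uses the 80% class. It should not be inferred that the PK results rest on misstated compliance. Subjects in the PK population apply the product at Day 0 and at the Week 4 visit, so for them the two windows coincide up to Week 4. This SAP governs the interim analysis only; SAP section 2 foresees a separate one for any final analysis.

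The figures assume nominal visit days and a 60 g tube content. The documents give no rate of self-stops, gaps or lost tubes. If the Safety population is the 7 treated subjects of SAP 6.1 (an assumption), one subject in the wrong class moves that row by 1/7 = 14.3 percentage points. One lost tube then lowers mean weekly dose by at most 7.5/7 = 1.1 g over the whole period, or 28/7 = 4.0 g up to Week 2.

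**What to change.** Use one window for both terms of the compliance formula.

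- Required days: planned dosing days from the start of the period to the period-end visit, or to the day before the Week 8 visit for the last period and for the overall figure. End at the date of trial withdrawal if the subject leaves earlier. Exclude only days of approved or investigator-directed discontinuation.
- Missed doses: required days in that window without an application, and no others.
- Extent of exposure: the number of days on which the product was actually applied.
- If no required days remain in a period, report compliance as not applicable.
- For a period with a used-but-lost tube, report the number of affected subjects. Show weekly dose either with those periods excluded or bounded by 0 to 60 g per lost tube.

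The cost is derivation wording and code. SAP 9.1 already names eCRF forms for application, missing doses, end of treatment and accountability. Some compliance figures will fall relative to the span-only reading, and a few dose values become missing or a range, which is a real loss in a small analysis set. SAP section 2 allows revision before the interim database lock. After that, the reading used should be explained in the study report, and the current wording should not be carried into a final-analysis SAP.

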6.2 Dosing Regimen

Subjects are to apply the IP topically once daily, preferably in the evening, for 8 weeks. The subject should apply enough IP to treat the entire affected areas and rub in gently to ensure that the plaques are saturated with the medication. Up to 3 tubes of 60 gram will be dispensed for a treatment period of two weeks including the allowed visit window of 2 days.

The IP is applied to affected areas on the:

- scalp
- trunk (including the neck)
- limbs
 - arms (including the back of the hands)
 - legs (including the buttocks and the top of the feet).

Only affected areas are to be treated. The subjects should therefore not continue treatment on a skin area which has been cleared but treatment may be restarted in case of recurrence at the subjects discretion (Section 6.3).

The face, genitals, and intertriginous areas should not be treated with the IP. The first application is done at Day 0 under the supervision and instruction of the trial staff. Subsequent applications will be applied by the subject or by the parent(s) or legal guardian(s).

All subjects are instructed to apply IP in the morning on the day before the Week 2, Week 4 and Week 8 visits. On the day of these visits, the subjects should not apply any IP before the visit.

Subjects are to record the date and time of application in the subject dosing diary (with the assistance of the parent(s) or legal guardian(s), as needed). The treated area should not exceed 30% of the BSA.

In case an AE reported in one area of the body lead the investigator to the decision to discontinue treatment this will apply for treatment in general and not only to the area for which the AE was reported.

Detailed application instructions will be provided in the subject instructions.

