6.7 Treatment Compliance

Records of trial product used, and dosages administered will be kept during the trial. The trial monitor will note product accountability during site visits and at the completion of the trial.

At all on-treatment visits, the subject will be asked if he/she has used the medication as prescribed. If this is not the case, the degree and nature of noncompliance will be specified. In addition, subjects will be asked to complete a dosing diary during the treatment period (with assistance from the parent(s) or legal guardian(s), if needed) as a measure of treatment compliance. Subjects who are consistently noncompliant will be counseled.

Subjects will be asked to return all used and unused tubes in the outer box at each visit. All returned tubes that had been dispensed to a subject will be weighed to determine the amount of the IP used per treatment phase.

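### SAP 9.1 puts the Week 2 and Week 4 visit day in the earlier period's days but a kit first used at that visit outside its grams, so period weekly dose is off by a few percent, and kits used across a visit have no stated handling

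*SAP*

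**What the plan says.** SAP section 9.1 reports exposure up to Week 2, up to Week 4, from Week 4 to Week 8 and overall. Weekly dose is total grams divided by duration in weeks, and "The total duration of exposure is defined as the time interval in days between the first dose and the last dose, inclusive, of study drug".

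**Days.** Period limits follow actual visit dates, and the "Week 2 (Week 4) visit date will be considered the last day of" the period that leads up to it.

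**Grams.** Each kit goes as a whole to a period according to its recorded use:
- "If the use period starts at Week 4 or Week 6 visit the time period is Week 4 to Week 8".
- A kit that starts before Week 2 (or Week 4) and is finished by that visit counts up to Week 2 (or Week 4).
- For any other kit, "otherwise time period cannot be determined".

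The protocol sets the timing of the visit-day dose. For Weeks 2, 4 and 8, section 6.2 says: "On the day of these visits, the subjects should not apply any IP before the visit". Section 6.7 adds: "Subjects will be asked to return all used and unused tubes in the outer box at each visit". Section 7.6.5 places the Week 4 application at the visit, after the pre-dose sample, and has no application on the Week 8 visit day.

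Neither document says which tube supplies the visit-day dose, or what happens to the grams of a kit with no period.

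**The concern.** A ratio needs its numerator and denominator to cover the same doses. If the visit-day dose comes from the newly dispensed kit, its day is counted before the visit and its grams after it. The earlier period's weekly dose is then too low and the later one too high, even when use is constant.

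The second gap is the kit with no period. If a programmer sums the remaining kits, grams drop out while every day stays in the denominator. The footnotes of Table 14.1.13.1 and Listing 16.2.5.1 mention only lost and unused tubes, so the table would not show the omission.

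At stake is the description of how much cream was used in the weeks before the Week 4 and Week 8 assessments. The interim analysis follows completion by 7 treated subjects, so one mishandled kit can visibly move a period summary.

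**Working it through.** The SAP gives no numeric weekly dose, so there is no stated figure to reproduce. The check counts doses and days under the section 9.1 rules.

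**Inputs.** Visits fall on Days 0, 14, 28 and 56, each post-baseline visit with a window of 2 days either way (Protocol Table 7-1). There is no dose on the Week 8 visit day.

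**Assumptions.** The subject applies one equal dose daily on Days 0 to 55, including the visit days, and uses kits only between consecutive visits. Up to Week 4 is read as cumulative. The tube used on a visit day is not stated, so both cases are shown.

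**Formula.** Reported weekly dose / true weekly dose = (doses whose grams are counted) / (days counted).

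| Period | Days counted | Grams counted, new kit on visit day | Ratio | Error | Range over visit windows |
|---|---|---|---|---|---|
| Up to Week 2 | Days 0–14 = 15 | Days 0–13 = 14 doses | 14/15 = 0.933 | -6.7% | -7.7% (12/13) to -5.9% (16/17) |
| Up to Week 4 | Days 0–28 = 29 | Days 0–27 = 28 doses | 28/29 = 0.966 | -3.4% | -3.7% (26/27) to -3.2% (30/31) |
| Week 4 to Week 8 | Days 29–55 = 27 | Days 28–55 = 28 doses | 28/27 = 1.037 | +3.7% | +3.2% (32/31) to +4.3% (24/23) |
| Overall | Days 0–55 = 56 | 56 doses | 56/56 = 1 | 0% | 0% |

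At an illustrative true 60 g/week, the three periods read 60 × 14/15 = 56.0, 60 × 28/29 = 57.9 and 60 × 28/27 = 62.2 g/week.

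**Old tube on the Week 4 visit day.** Up to Week 4 becomes 29/29 and Week 4 to Week 8 becomes 27/27, so there is no error in either. The Week 2 error remains unless the Week 2 visit-day dose also comes from the old tube.

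**Which tube is likely.** At Week 2 no on-site application is scheduled, evening use is preferred, and the old tubes are due back at the visit. The dose later that day would ordinarily come from the new kit. At Week 4 the dose is applied on site and could come from either.

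**Kits used across a visit.**
- Across Week 4: the kit starts before Week 4 and ends after it, meets neither assignment rule, and belongs to no period.
- Across Week 2, finished by Week 4: it counts in full up to Week 4 and is missing only from up to Week 2.
- Started at Week 4 and used across Week 6: it counts in full in Week 4 to Week 8.

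**Size if grams are summed without the kit.** Suppose 50 g was used evenly across Week 4 at a true 60 g/week. Each side holds 28 × 60/7 = 240 g under the new-kit case and loses 25 g, or 25/240 = 10.4%. Combined with the day shift:
- Up to Week 4: 215 / (29/7) = 51.9 g/week, -13.5%.
- Week 4 to Week 8: 215 / (27/7) = 55.7 g/week, -7.1%.

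With the old tube on the visit day, the losses are 25/248.6 = 10.1% and 25/231.4 = 10.8%. Both sides of Week 4 are understated in either case.

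**The case against.** The strongest objection is that the tube supplying the visit-day dose is an assumption. Section 6.7 says tubes come back at each visit, but not whether that happens before or after an on-site application. This stands for Week 4. A reader might infer a definite spurious rise in use after Week 4 of 7.4% (29/27 = 1.074), but the documents support it only if the new kit was used on site. For Week 2 the objection is weak, for the reasons given above.

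A reader might also infer that a kit crossing a visit contributes nothing to any period, or that it enters as 0 g. The first is wrong for kits that cross Week 2 and finish by Week 4, and for kits that cross Week 6. The second is one reading of a silent rule. The tables define n as the number of valid measurements, so a missing period dose fits the SAP equally well. A dropped Week 4 kit can also turn the Week 4 to Week 8 overstatement into an understatement, so no single direction of error can be claimed for that period. Such a kit arises only if the return instruction was not followed, and its frequency is unknown.

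Finally, the affected tables are descriptive. Section 2.3 of the protocol ties maximum use to disease severity and body surface area, not to grams per week. Listings 16.2.5.1 and 16.2.5.4 show doses by period and kit details by subject, so a reader can look behind the table. This limits the importance of the point but does not remove the mismatch.

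**Conclusion.** The mismatch between days and grams is real but small. Followed as written, section 9.1 understates the up-to-Week-2 weekly dose by about 6.7% for a constant daily user who takes the visit-day dose from the new kit, as the protocol's timing and return rules make likely. At Week 4 the errors are -3.4% and +3.7% if the new kit supplies the on-site dose, and zero if the old tube does. Week 6 is not a period boundary and no dose is due on the Week 8 visit day, so no other visit is affected. The overall weekly dose has no day shift.

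Separately, the SAP leaves open how a kit without a period is handled. A sum without it would understate both sides of Week 4, by about 7% to 14% in the example above, which rests on an assumed 50 g kit used evenly.

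A reader might conclude that the primary results or the maximum-use claim are undermined. The documents do not support that: the HPA, calcium and PK endpoints do not use period weekly dose.

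**What to change.** For the period weekly dose only, amend SAP section 9.1 as follows.

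1. **Same boundary for days and grams.** When the visit-day dose comes from the newly dispensed kit, end the earlier period's days on the day before the visit and start the later period on the visit day. Make this the default at Week 2. At Week 4, follow the tube recorded as used on site; if it is not recorded, state the assumption. In the new-kit case the ratios become 14/14, 28/28 and 28/28.
2. **Unassigned kits.** Where a used kit cannot be assigned to a period, set that subject's dose and weekly dose for the affected period to missing, and say so in a table footnote. A kit crossing Week 2 but finished by Week 4 affects only up to Week 2. Splitting its grams by days is less safe, because it assumes even use while cleared areas are left untreated.

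The cost is SAP wording and a few lines of code. SAP section 2 allows revisions before the interim database lock; after that, the change can be explained in the study report and carried into the SAP for any final analysis. The downside is a few missing period values, and a residual error at Week 4 if the tube assumption is wrong: 29/28 = +3.6% before and 27/28 = -3.6% after. Listing 16.2.5.4 shows use by kit, not by dose, so it may not settle which tube was used that day.
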